8.3 Statistical Power Considerations

According to the sample size calculation (section 3.2) the actual expected power is 80.8%.

Seite 36 von 54

Protocol 990211 RAMOSA

RFA for multi-level OSA

Protocol version 6.0 from 26th September 2014

8.4 Analysis Sets

The following defines the analytic sample for the relevant endpoint used in a particular analysis.

Safety Analysis Set (SAS): The safety analysis set will include all subjects who receive radiofrequency treatment.

Full Analysis Set (FAS): The full analysis set will include all subjects who receive radiofrequency treatment and completed all 8 visits of the study.

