3.1.2 Subjects included in the Primary Efficacy Objective Analysis

The primary efficacy analysis will include all subjects who received all three radiofrequency treatment procedures and the follow-up assessment at 6-months post-treatment.

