5.6 Visit 6 - Follow-Up Visit (6 weeks later)

The patient will undergo complete post-treatment evaluations including sleep history and physical examination (including height, weight, and blood pressure) as done in Baseline Visit. The patient will be asked to complete questionnaires including Epworth Sleepiness Scale (ESS), Functional Outcomes of Sleep Questionnaire (FOSQ) and 10 cm VAS concerning pain, snoring (bed partner), speech, and swallowing. The study physician will inform the patient on his/her study results and medical condition and will give recommendations for ongoing management as needed.

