5.8 Visit 8 – Final Study Visit (after the PSG sleep study)

Shortly after the 2nd PSG study, the study physician will inform the patient on his/her study results and medical condition and will give recommendations for ongoing management as needed.

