6 DURATION

This study has a minimum of eight visits. The first visit, the Screening Visit, is planned for determining whether patient qualifies for the study. This visit will take up to 1 hour. In the second visit, the Baseline Visit, which occurs up to 2 weeks later, standard medical history, demographics and various questionnaires will be obtained from the patient. In addition, the patient will undergo a Müller's Maneuver and will be sent to the sleep lab for a PSG study (one night). This visit will last about 60 minutes.

The third visit is the first RF treatment session and will last about 1 hour. The fourth and fifth visits involve additional RF treatments and will last about one hour each. The first follow-up visit will occur 6 weeks after the third treatment visit and will last as well about 1 hour. The 7th visit, the 6-month follow-up visit, will occur 6 months later and will be no more than 1 hour. At the end of this visit the patient will be admitted to a sleep labor for undergoing the 2nd PSG study. Finally, the 8th and final Visit will last about 30 minutes. The patients may require additional visits in case of complications that are needed to be treated in the hospital or if they have a question or concern. The entire duration of the study for an individual patient is no longer than 24 weeks plus 6 months of follow-up.

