7 INSTRUMENTS

The following outcome measures will be utilized to represent meaningful measurements of therapy success:

1. Apnea-hypopnea index (AHI) - is an index of sleep apnea severity that combines the frequency of apnea and hypopnea events. The severity of obstructive sleep apnea is determined by the measurement of apneas and hypopneas. An obstructive apnea is defined as a cessation (> 90% decrease) of airflow for at least 10 seconds with breathing effort; and a hypopnea is defined as an event with at least a 30% reduction in airflow lasting at least 10 seconds, and with $\geq 4\%$ oxygen desaturation. The frequency of apneas and hypopneas per hour of sleep is termed the apnea-hypopnea index (AHI). AHI values are typically categorized as 5–15/hr = mild; 15–30/hr = moderate; and $> 30/h$ = severe. AHI will be determined at baseline and at the 6-months follow-up visit.
2. Oxygen Desaturation Index (ODI) – ODI is defined as the number oxygen desaturation events, where there is a $\geq 4\%$ desaturation from pre-event baseline, that occur per hour of sleep. ODI generally correlates well with AHI [15], and it is reasonable to conclude that a 25% reduction in ODI represents a

Seite 34 von 54

Protocol 990211 RAMOSA

RFA for multi-level OSA

Protocol version 6.0 from 26th September 2014

clinically meaningful improvement. ODI will be determined at baseline and at the 6 months follow-up visit.

3. Epworth Sleepiness Scale (ESS) - The ESS is a validated, self-report instrument that rates a subject's tendency to fall asleep in eight common daily situations. The ESS Scale has been validated primarily in OSA. It is used to measure excessive daytime sleepiness, and is often utilized before and after the administration of treatment (e.g. CPAP) to document improvement of symptoms. The patient will complete this questionnaire at the Baseline, at Visit 3 (prior to the 1st RFA treatment), Visit 4 (prior to the 2nd RFA treatment), at Visit 5 (prior to the 3rd RFA treatment), at Visit 6 (6 weeks follow-up post 3rd RFA treatment), and at Visit 7 (6 months follow-up).

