8.1 Primary Efficacy Endpoint

The primary endpoint of AHI and ODI obtained at the 6-month follow-up will be compared to the Baseline measurement. The subject is a responder if the reduction in AHI is $\geq 50\%$, and ODI reduction is $\geq 25\%$. The proportion of subjects meeting the responder criteria among all included subjects will be evaluated using a one-sided 95% confidence interval. In addition one sample test of the proportion of patients meeting the PG at 6month is significantly different than 50%. The study is designed to demonstrate success rate of 20% beyond the PG of 50%. Proportion with 95% CI will be given using normal approximation to the Binomial. P-Value will be derived based on the exact binomial distribution of the null hypothesis, that is assuming $p=0.5$.

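### The Full Analysis Set (8.4) requires all eight visits, the primary efficacy population (3.1.2) does not, and the plan never says which of them supplies the denominator in 8.1

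*Combined protocol and SAP*

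**What the plan says.** Section 8.4 introduces its sets with the statement "The following defines the analytic sample for the relevant endpoint used in a particular analysis". It lists two, a safety set and the FAS, so the FAS is its only efficacy set: "The full analysis set will include all subjects who receive radiofrequency treatment and completed all 8 visits of the study".

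Section 3.1.2 sets a different condition: "The primary efficacy analysis will include all subjects who received all three radiofrequency treatment procedures and the follow-up assessment at 6-months post-treatment". Visits 6 and 8 are not mentioned.

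Section 8.1 gives the test without naming a set: "The proportion of subjects meeting the responder criteria among all included subjects will be evaluated using a one-sided 95% confidence interval". Section 8.2 adds intention-to-treat and as-treated analyses of all enrolled subjects.

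The primary endpoint uses two measurement occasions only. Section 7 says "AHI will be determined at baseline and at the 6-months follow-up visit", and has the same timing for ODI. Visit 6 (5.6) consists of "complete post-treatment evaluations including sleep history and physical examination" plus questionnaires and visual analogue scales. Visit 8 (5.8) comes after the endpoint PSG: "Shortly after the 2nd PSG study, the study physician will inform the patient on his/her study results and medical condition". Appendix I adds a physical examination, an adverse event form and an end-of-study form at Visit 8.

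**The concern.** Take a subject who had all three treatments and both PSGs but missed Visit 6 or Visit 8. Responder status is fully observed. Section 3.1.2 keeps this subject and the FAS removes the subject. The non-responder rules in 3.1.1 and 8.5 do not settle the matter: they cover death, failed treatment attempts, alternative treatment, leaving the study and loss to follow-up, not one missed visit in a subject who has the endpoint.

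Two things are at stake. First, an efficacy set that depends on Visit 8 selects subjects on an event that follows the outcome. If attendance is related to response, the responder rate is biased. Second, the study is open-label and single-arm, so two defensible denominators leave room to choose between them once outcomes are known.

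**Working it through.** **Inputs.** From 3.2: n = 43, performance goal p0 = 0.50, alternative p1 = 0.70, reject if Z ≥ 1.96. From 8.1: p-value from the exact binomial at p = 0.5, and a one-sided 95% interval by normal approximation. From 3.1: a one-sided 97.5% interval. Because the plan states both levels, results are read at 0.025 and at 0.05.

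**1. The plan's own figures.** Z = (r/n − 0.5)/√(0.25/n). At n = 43 the denominator is 0.0763, so r = 28 gives Z = 1.98 and r = 27 gives Z = 1.68. At least 28 responders are needed. P(X ≥ 28 | 43, 0.5) = 0.0330 and P(X ≥ 28 | 43, 0.7) = 0.8081. Both match 3.2, and the power matches 8.3.

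**2. The two definitions applied to the same subjects.**

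| Subject with three treatments and both PSGs | 3.1.2 | FAS (8.4) |
|---|---|---|
| attended all 8 visits | in | in |
| missed Visit 6 only | in | out |
| missed Visit 8 only | in | out |

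**3. Can the choice change the result?** The missed visits below are assumed.

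| Case | r/n | Rate | Z | Exact one-sided p |
|---|---|---|---|---|
| A, by 3.1.2 | 27/43 | 62.8% | 1.68 | 0.063 |
| A, by FAS: 4 non-responders miss a visit | 27/39 | 69.2% | 2.40 | 0.012 |
| B, by 3.1.2 | 28/43 | 65.1% | 1.98 | 0.033 |
| B, by FAS: 2 responders miss a visit | 26/41 | 63.4% | 1.72 | 0.059 |

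Case A turns failure into success by the exact p-value at 0.025 and at 0.05, and by the Z ≥ 1.96 rule. Case B turns success into failure by the Z rule and by the exact p-value at 0.05; at 0.025 the exact test fails either way.

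One reading shows no reversal. By the normal-approximation one-sided 95% limit, 27/43 already clears 50%: 0.6279 − 1.645 × √(0.6279 × 0.3721/43) = 0.507. So does 26/41: 0.6341 − 1.645 × √(0.6341 × 0.3659/41) = 0.510.

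**4. Power.** If k of the 43 are lost regardless of outcome, the Z rule gives:

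| k | n | Responders needed | Power at 70% | Actual alpha |
|---|---|---|---|---|
| 0 | 43 | 28 | 0.808 | 0.033 |
| 2 | 41 | 27 | 0.776 | 0.030 |
| 4 | 39 | 26 | 0.740 | 0.027 |
| 6 | 37 | 25 | 0.698 | 0.024 |

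These falls are not all lost information, because actual alpha falls too. Adding subjects to 43 also lowers power under this rule: 0.778 at n = 44 and 0.746 at n = 45.

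**5. Outcome-related attendance**, by exact enumeration from 43 under the Z rule. If 10% of responders and no non-responders miss a visit, power at 70% is 0.621. If 10% of non-responders and no responders do, the one-sided error at a true 50% is 0.052 instead of 0.033. Both rates are assumptions.

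**The case against.** The strongest reply is that nothing assigns the FAS to the primary test. Section 3.1.2 is headed as the population for the primary efficacy objective and keeps this subject, and the wording of 8.1 can be read as pointing back to it. That stands. A reader might infer that such subjects are dropped from the primary analysis; the documents support this only for the FAS. They do not settle the primary test, because 8.4 says that its sets define the sample for each endpoint and offers no other efficacy set.

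Several further points also stand:

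- The smallest apparent flip, 28/43 to 27/42 when one responder is lost, appears under Z ≥ 1.96 (1.98 against 1.85) but not under the exact test in 8.1. There p is 0.033 and 0.044, so both fail at 0.025 and both pass at 0.05. It should not be relied on.
- Much of the apparent power loss is discreteness. With 5% missing at random, power is 0.747, but size also falls from 0.033 to 0.025. The 48 enrolled include a 10% dropout allowance, which might absorb some missed visits.
- The study in 2.5 whose returning patients were mostly symptomatic concerns return for a follow-up PSG, with free further treatment on offer. It is not evidence about a six-week visit or a results visit. Its direction would lower the FAS responder rate, the opposite of case A.
- Visit 8 is more than a conversation about results (Appendix I), and Visit 6 is the comparison time point for the paired tests in 8.2. An all-visits set may have a use there, but neither visit contributes to responder status.

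**Conclusion.** The concern holds as an unresolved conflict between 8.4 and 3.1.2. As written, the FAS excludes subjects whose primary outcome is known, partly because of attendance after that outcome was measured, and no section says whether the FAS or the 3.1.2 population governs 8.1. The choice can reverse the trial's conclusion: 27/43 (exact p = 0.063) against 27/39 (p = 0.012). This rests on an assumed four non-responders missing a visit and on the exact p-value or the Z rule; the one-sided 95% normal-approximation limit does not reverse. The documents give no miss rates by visit, so the example shows what is possible, not what is likely. Neither a power loss nor a direction of bias for the primary test can be claimed from the text. The stated sample size and power are not wrong on this account.

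**What to change.** In 8.4, delete the condition that all eight visits be completed. State that missing Visit 6 or Visit 8 does not exclude a subject from the primary analysis. Name one primary set and use that name in 3.1.2, 8.1 and 8.4. Score subjects with a baseline and a 6-month PSG on those recordings unless a non-responder rule in 3.1.1 applies; some of those rules hold whatever the 6-month AHI. If an all-visits set is wanted, call it per-protocol.

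With the condition deleted, the FAS wording becomes that of the safety set, which is wider than 3.1.2. The named set must therefore be reconciled with 3.1.1 and 8.5, which count as failures some subjects whom a completer definition leaves out. That is a separate decision and should be made in the same revision.

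The cost is wording in 8.4, cross-references in 3.1.2 and 8.1, and that reconciliation. No new data or visits are needed, and it should be done before outcomes are examined.

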8.5 Handling of Missing Data, Subject Withdrawals, and Treatment Failures

Subjects that are lost-to-follow-up will be categorized as treatment failures from the time point of dropout forward. Sensitivity analyses will also be conducted excluding lost-to-follow-up subjects to see what impact, if any, they might have on the overall results of clinical activity. Time-to-event analyses will consider these subjects as censored at the lost-to-follow-up time point. All data will be recorded on a CRF forms and will be subjected to regular monitoring.

Every effort will be made to follow subjects for study observation and encourage compliance with study measurements to minimize the amount of missing data.

8.6 Interim Analyses

There are formal interim analyses planned for the first 15 patients and then every 15 completed patients. Review of safety data will be evaluated on a continual basis throughout the study. Review of safety data by a Clinical Research Office (CRO) for the purpose of general safety review will be done; however, the review of such data is not intended to impact the study conduct unless there are safety concerns. As such, it is expected that the trial will continue to its scheduled completion barring any unexpected safety issues.

9 RISK ANALYSIS

9.1 Risks of Confidentiality

(1) Each patient at the time of enrollment will be assigned a subject number. The codebook linking the patient identifiers to the subject number will be keep in a locked cabinet in the locked office of each Principal Investigator. The subject number is the number that will appear on all study related documents.

(2) Study staff will be trained on the importance of confidentiality. All medical information recorded as part of the study will be captured using pre-printed standardized forms (Case Report Forms) specific to the study. The only identifier on the forms will be the subject study number. The forms for a given subject will be kept in individual study folders and stored in a locked cabinet in the locked office of the study coordinator.

(3) All adverse events and serious adverse events will be documented in the subject study folder. Serious adverse events will be immediately communicated to the institutional IRB per standard protocol.

9.2 Risks and Discomforts

The direct risks of radiofrequency ablation of upper airway tissues include the following:

(1) Risk of bleeding - The use of a probe inserted into upper airway tissues will result in minor bleeding. The amount of bleeding is minimal due to the use of epinephrine and the superficial nature of the procedure. Bleeding, if present, can be controlled with pressure, silver nitrate cautery, and/or suture ligature. All surgeons will have many years of experience with radiofrequency ablation.

(2) Risk of pain or discomfort - Needle and probe insertion into the tissue will cause mild pain and discomfort that is typically well tolerated in an awake patient. The patient will be given topical anesthetic and a local anesthetic of lidocaine prior to the procedure, and is therefore expected to have minimal discomfort.

(3) Risk of hematoma - The use of a needle and probe will result in some bleeding and the possibility of hematoma (swelling of blood or clot) formation. The risk of this uncommon complication is expected to be minimal, and the use of epinephrine in the lidocaine additionally reduces the risk of hematoma formation. Observed hematomas will be drained under local anesthesia in order to prevent breathing or swallowing issues.

(4) Risk of infection or abscess - The procedure involves penetrating tissue with the probe which has the potential risk of infection. This risk is minimized by the use of antibiotics and steroids after each treatment. Patients will be followed closely after the procedure to assess for signs and symptoms of infection and/or abscess.

(5) Nerve Trauma - This is a theoretical risk since the application of the RFA energy will be applied far from the natural landmarks of the lingual and hypoglossal nerves.

(6) Dysphagia - Slight difficulty in swallowing is common but all patients are expected to resume at least a diet of soft foods immediately following the procedure. It is anticipated that all patients will resume a normal diet by post-procedure day 3.

(7) Procedure Duration- This is a theoretical risk. However, the CelonProSleep *plus* has a built-in automatic turn-off system shuts off after delivering certain amount of energy.

(8) Other risks may include airway problems, nasopharyngeal stenosis, ulceration of the treated site, paresthesias, edema of tongue, change in speech, and other possible unexpected symptoms.

9.3 Minimization of Risk to the Patient

Risks can be minimized through the use of proper surgical procedures, compliance with this protocol and device specifications, adherence to the guidelines for patient selection, close monitoring of the

subjects' physiologic status during treatment and follow-up procedures, and by promptly supplying the Sponsor with all pertinent information required by this protocol.

The surgical risks are minimized in this study by including OSA subjects who do not have significant co-morbidities, utilizing surgeons who have previous clinical experience and thorough protocol related training prior to initiation of the clinical trial. RAMOSA study surgeons must be familiar with neck surgery, the tongue and pharyngeal muscle movements, and have previously used RFA in the treatment of snoring.

Additional measures will be taken to minimize risk to subjects as part of this investigational plan:

- Reported adverse events will be reviewed regularly and reported to the sponsor throughout the study. Any severe adverse event will be reported to the institutional IRB and sponsor in a timely fashion. Appropriate medical measures will be immediately taken to resolve all adverse events.

9.4 Potential Benefits

Although no assurances or guarantees can be made, there is a reasonable expectation that the use of radiofrequency ablation may be beneficial. Radiofrequency ablation (RFA) of the upper airway using FDA-cleared devices has demonstrated promise as a treatment alternative for obstructive sleep apnea in multiple published studies ^{29-31, 34}. In these studies, repeated RFA of the soft palate and base of tongue region resulted in significant reductions in AHI and daytime sleepiness without significant complications. RFA has several advantages over traditional surgical approaches including its ability to address multiple levels of the airway (nose, palate, tongue); ability to perform in the office under local anesthesia; lower cost; and minimal pain and morbidity. The CelonProSleep *plus*, the study device used in this study, is similar to other FDA-cleared RFA devices (e.g. Gyros or Somnos) but delivers the RF energy more rapidly thereby adding to patient comfort during the procedure. In addition, due to the bipolar electrode the CelonProSleep *plus* device coagulates much faster (although the power setting is less) than the Gyrus or Somnos systems. Therefore, less energy is needed to reach the coagulation threshold of the tissue.

10 ADVERSE EVENT MANAGEMENT

Timely, accurate, and complete reporting and analysis of safety information for clinical studies is crucial for the protection of subjects, Investigators, and Sponsor. Data collected in this study may be used in support of global regulatory approvals. Sponsor has established procedures in conformity with worldwide regulatory requirements to ensure appropriate reporting of safety information. This study is conducted in accordance with these procedures and regulations. All adverse events and adverse device effects will be reported to all Institutional Review Boards (IRB's). At each evaluation, the investigator will determine whether any adverse events (AEs) have occurred. Detailed information regarding such adverse events will be recorded on a specific case report form (CRF) for adverse events. Investigators will be asked to make a judgment as to the relationship of the event to the study device. Follow-up data to ascertain the existence of residual effects from the event will be obtained.

10.1 Definitions

For the purpose of this protocol, the following definitions shall apply:

10.1.1 Adverse Event (AE)

An adverse event (AE) is any untoward medical occurrence in a subject (without taking into account the relationship with the device under investigation). The AE can be any unfavorable or unintended sign, symptom, or disease temporally associated with the use of the device (ICH E2A). All new and/or worsening adverse events (AE) will be collected throughout the study duration, starting when the subject is enrolled into the study (when the Subject Informed Consent is signed) and reported to the Sponsor on an Adverse Event Case Report Form. In addition, all deaths must be reported. Documented pre-existing conditions are not considered adverse events unless there is a change in the nature or severity of the condition and required additional medical or pharmacological treatment.

All adverse events should be followed until the adverse event has been resolved, is ongoing with no further actions to be taken, the subject exits the study or until study closure, whichever occurs first. Investigators will categorize AE's according to their severity and relatedness (e.g., to the surgical procedure, to the CelonProSleep plus, etc.). The Sponsor will then review all reported adverse events for completeness, and ask for clarification or additional information if necessary.

AE Definitions for Investigator Classification

Investigators are responsible to categorize adverse events according to their seriousness and relatedness. The definitions for classifications are included below. Those events that do not meet the criteria for Serious Adverse Event are considered non-serious.

